2.3.9 Compliance

We will conduct a Complier Average Causal Effects (CACE) analysis using an instrumental variable framework to explore the impact of compliance on the primary outcomes at different levels of compliance. The CACE analysis will be implemented using a two-stage least squares (2SLS) approach clustering the standard errors, where the first stage models compliance as a function of the randomised treatment assignment, and the second stage models the outcome as a function of the predicted compliance from the first stage and other covariates.

Compliance will be measured at the school level through a binary variable, compliance (Yes/No). Compliance for those schools in the intervention arm will be assessed based on the level of engagement. Section 5 discusses the engagement tool in more detail. The tool assesses engagement across five key dimensions:

- Individual Training,
- Whole Staff Training,
- Consultancy,
- Reflective Supervision,
- Webinars.

Each dimension is scored based on specific criteria, such as the number of staff trained, attendance at meetings, and utilisation of resources. The tool uses a point-based system, with 100 points possible across all dimensions. The final engagement score is calculated as a percentage, with clear thresholds for interpretation:

- up to 50% indicates poor engagement,
- 51-75% moderate engagement,
- 76-90% good engagement, and

- 90-100% excellent engagement.

The engagement score will be used to measure compliance in the CACE analysis. CACE weighs the intention-to-treat (ITT) treatment effect by the proportion of compliance, allowing for the estimation of unbiased treatment effects while maintaining the original randomisation in the analysis. Therefore, a school in the intervention arm will be considered compliant with the trial if showing an engagement of 76% or higher. As a robustness check in the analysis, we will explore how compliance is associated with the outcomes and if any threshold for minimum compliance emerges by setting compliance at 76%, 80% and 90% of the engagement tool. This finding could serve in the future of a trial to establish a minimum threshold that ensures a successful delivery.

As set out in the TOC, the impact on CYP is mediated through a change in policies and procedures at the school level. Measuring compliance on that aspect remains challenging. However, this mediator will be assessed qualitatively through the IPE data collection activities.

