Duration of support (1:1 interview): Variation in the length of intensive support from staff members to students.

Prior support provision (1:1 interview): We aim to select a mix of students who either received relevant support for the first time after implementation of TISUK and those who were receiving pastoral support or other counsel prior.

Engagement

¹⁶ Case studies will be undertaken in 2025. Students were in Year 8 at the start of the evaluation, and match the cohort (in age) of the efficacy trial.

The quantitative data from the delivery team will be used to populate an engagement tool that assigns a score at the school level. This tool employs a comprehensive scoring system to evaluate the extent of each school's engagement with the intervention and their level of compliance.

It consists of five key dimensions, each weighted differently to reflect their relative importance in the overall implementation:

1. Individual Training (45 points): This dimension assesses the number of staff who have completed specialised training courses, specifically the SLT (Specialist Leader of Teaching) and Diploma courses. The scoring ranges from 0 points (no staff trained) to 30 points (optimal ratio of trained staff to pupils), with intermediate scores based on the number and type of staff trained.
2. Whole Staff Training (25 points): This evaluates the extent of training the entire staff receives. Points are awarded based on the number of completed training hours, ranging from 0 points for no training to 25 points for the full 6 hours.
3. Consultancy (15 points): This dimension measures attendance at termly meetings and adherence to guidelines for staff involvement. It is divided into two sub-components: attendance at meetings (up to 10 points) and following staff involvement guidelines (up to 5 points).
4. Reflective Supervision (10 points): This assesses staff participation in reflective supervision training. Points are awarded based on the number of training days completed, from 0 points for no attendance to 10 points for completing all four training days.
5. Webinars (5 points): This dimension evaluates the utilisation of provided webinars by the school. Schools can receive 0 points for no webinar use, 3 points for viewing 1-3 webinars, or 5 points for viewing all four webinars.

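### Moving the compliance cut from 76% to 80% to 90% cannot reveal a delivery threshold, because the CACE grows with the cut by construction; the 76% estimate also rests on an unstated assumption

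*SAP*

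**What the plan says.** SAP 2.3.9 (Compliance) sets out the estimator: "The CACE analysis will be implemented using a two-stage least squares (2SLS) approach clustering the standard errors", with random allocation as the instrument in the first stage. The exposure is a flag: "Compliance will be measured at the school level through a binary variable, compliance (Yes/No"). The main cut is fixed: "a school in the intervention arm will be considered compliant with the trial if showing an engagement of 76% or higher". The SAP describes the estimator in these terms: "CACE weighs the intention-to-treat (ITT) treatment effect by the proportion of compliance", and says that this gives unbiased treatment effects.

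As a robustness check, the plan then examines how compliance relates to the outcomes and "if any threshold for minimum compliance emerges by setting compliance at 76%, 80% and 90% of the engagement tool". It gives the result a use beyond this trial: "This finding could serve in the future of a trial to establish a minimum threshold that ensures a successful delivery". Protocol 4.1 (Compliance) contains the same plan.

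The score comes from the engagement tool in protocol 5.2 (Engagement) and Appendix 3. Two of its five dimensions carry most of the points: "Individual Training (45 points") and "Whole Staff Training (25 points"), out of 100. Both documents label scores of 51-75% as moderate engagement.

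**The concern.** There are two separate problems.

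The first is the search over cuts. Changing the cut changes only the denominator of the estimator. A rising series of CACEs at 76%, 80% and 90% would look like a dose threshold, but it would appear with any dose-response, including none. A team that took it as a finding could carry an unsupported minimum-delivery standard into a later trial.

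The second is the 76% estimate itself. The flag gives an intervention school scoring 75% the same value as a control school. The model then assumes that being allocated to the programme changed nothing for pupils in that school. This is the exclusion restriction, and the SAP does not state it. If partial delivery has some effect in the same direction, that effect is credited to the schools above the cut and the CACE is biased away from zero.

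**Working it through.** **1. Illustrative ITT.** The documents state no CACE and no compliance share, so I use the MDES in the Randomisation column of SAP Table 4, 0.094 SD, as the ITT. It can be reproduced closely. The SAP 2.2 formula without covariates is MDES = M × sqrt[ρ/(P(1−P)J) + (1−ρ)/(P(1−P)Jm)].
- Randomisation column (J = 78, P = 40/78, m = 166, ρ = 0.015): 0.0930 with t on 76 df, 0.0918 with normal quantiles; stated 0.094.
- Protocol column (J = 100, P = 0.5, m = 160, ρ = 0.03): 0.1064 with normal quantiles, as stated.

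**2. The estimator.** There is one instrument and one binary exposure. I take control schools as 0, since only intervention schools are scored. Covariates and unequal school sizes aside, CACE(c) = ITT / p(c), where p(c) is the share of intervention schools scoring at least c. The ITT does not involve c. Because p(76) ≥ p(80) ≥ p(90), it follows that |CACE(76)| ≤ |CACE(80)| ≤ |CACE(90)|. The inequality is strict when the ITT is not zero and some school scores between the cuts.

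**3. Size.** Shares are assumed, out of the 40 intervention schools in SAP Table 4; ITT = 0.094.

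| Schools at or above 76/80/90 | Shares | CACE at 76/80/90 |
|---|---|---|
| 34/31/22 | 85/77.5/55% | 0.111/0.121/0.171 |
| 28/24/14 | 70/60/35% | 0.134/0.157/0.269 |
| 20/16/8 | 50/40/20% | 0.188/0.235/0.470 |

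**4. Could the procedure find a threshold?** This was simulated at school level: 4,000 runs, 40 against 38 schools, m = 166, ICC 0.015. The four schools that withdrew from the intervention arm (SAP 2.2) were set to score 0. The other 36 scored 60, 70, 78, 85 or 95 with probabilities 0.10, 0.10, 0.12, 0.28 and 0.40. All scores are assumptions. Mean shares above the cuts were about 72/61/36%.

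| True pattern | Mean CACE at 76/80/90 | Mean t at 76/80/90 |
|---|---|---|
| 0.10 in all 36 schools, no threshold | 0.1269/0.1504/0.2641 | 2.728/2.649/2.359 |
| 0.10 only at 76 or above | 0.1005/0.1188/0.2081 | 2.250/2.195/1.990 |
| 0.10 × score/100 | 0.1071/0.1268/0.2209 | 2.341/2.295/2.094 |
| No effect | −0.0001/−0.0001/0.0000 | −0.001/0.000/0.000 |

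The absolute CACE rose across the cuts in every run. With no threshold, the chance of an estimate of 0.20 SD or more in absolute size went from 6% to 19% to 70%. With a real threshold at 76%, the estimate kept climbing past it. The standard error grows along with the estimate (0.047/0.057/0.112 in the first row), so a higher cut adds no evidence.

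**5. The 76% assumption against the tool.** Full Individual Training (45) plus full Whole Staff Training (25) is 70. One or two consultancy meetings add 5 (Appendix 3), making 75. Such a school is coded like a control school. If its pupils benefit, the estimate overshoots: the first row of the table gives 0.127 against a true 0.10. In the proportional row, schools at 76 or above have a mean score of (0.12×78 + 0.28×85 + 0.40×95)/0.80 = 88.95, so their true effect is 0.089, against an estimate of 0.107.

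**6. The score as exposure.** Here the estimate at full engagement is ITT / mean(score/100). Suppose the benefit, d, occurs only at 76 or above. With half the schools there and a mean score of 70 (assumed), this gives 0.50d/0.70 = 0.71d; with 36% and a mean of 65 (assumed), 0.36d/0.65 = 0.55d. With the step 4 scores, the mean is 0.9 × 84.16 = 75.7, giving 0.72d/0.757 = 0.95d. For a flat 0.10 in the 36 schools, it gives 0.09/0.757 = 0.119, an overstatement.

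**The case against.** The best defence is that the plan is modest. The cuts are called a robustness check, the verbs are tentative, no decision rule is given, and the analysis also looks more generally at how compliance relates to outcomes. That stands. A reader might infer that the team will certainly declare a threshold from rising CACEs, and the text does not say so. It does name finding a threshold as the aim and gives it a future use, and the procedure cannot serve that aim.

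A reader might also infer that the 76% CACE is certainly inflated. The documents do not support that. Protocol section 1 argues that training alone is unlikely to be enough and that a comprehensive approach is needed. If little happens below 76%, that cut may be reasonable, and in the second row of the simulation it recovers the true 0.10. The bias is conditional.

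Much larger CACEs follow if very few schools are assumed to pass 90%. No scores are reported, and the protocol's risk table points towards high attendance: full attendance is expected, missed sessions can be made up, and diploma delegates are said nearly always to finish. These are expectations, not data, so only a range is defensible.

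Finally, it is tempting to replace the flag with the continuous score. The score model is a different assumption, not a weaker one. The points were set by the evaluation, and their spacing is arbitrary: reflective supervision earns 2, 4, 8 or 10 for one to four days, and one or two consultancy meetings both earn 5. It belongs beside the 76% analysis.

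**Conclusion.** The concern holds for the threshold search. That |CACE| cannot fall as the cut rises follows from the estimator and needs no assumption about dose-response; an estimate near zero stays near zero. The size depends on shares that the documents do not give. With an ITT of 0.094, the 90% CACE is about 1.5 times the 76% CACE when engagement is high (0.171/0.111) and 2.5 times when it is low (0.470/0.188).

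For the 76% estimate the conclusion is conditional. The claim of unbiasedness needs the exclusion restriction. The tool's scoring makes a failure plausible, and the direction is away from zero if partial delivery helps.

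One might read this as a threat to the trial's main result. It is not: the ITT analysis does not use the flag, and a higher cut does not strengthen the test. The matter is the interpretation of a secondary analysis, worth correcting because its result is meant to inform later trials.

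**What to change.** - In SAP 2.3.9 and protocol 4.1, delete the inference of a minimum threshold from CACEs at different cuts, and the sentence on using it in future trials. If the three cuts are kept, report the compliant share beside each estimate and state that the rise is mechanical.
- State the exclusion restriction for the 76% CACE (no effect of allocation in intervention schools below 76%) and make the claim of unbiasedness conditional on it.
- Add a two-stage least squares sensitivity analysis with the 0-100 engagement score as exposure (control schools 0, withdrawn schools the score they reached), instrumented by allocation with school-clustered standard errors. Report it alongside the 76% version.

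The cost is wording in two documents and one extra model; the score is already planned. The downside is that the score model assumes an effect proportional to the points and understates the effect at full engagement if benefit occurs only at 76% or above (step 6). That limitation should be stated with the result.

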2.3.10 Intra-cluster correlations (ICCs)

In this trial, the units forming clusters are schools. The Intraclass Correlation Coefficients (ICCs) will be computed for the baseline measure of the primary outcome, externalising behaviour, using an empty multilevel model without covariates. The ICC will be estimated at the school level, as this is the clustering level in the study design.

Specifically, a two-level random intercept model will be fitted, with children and young people (CYP) at level 1 nested within schools at level 2. The ICC will be calculated using the following formula:

$$ICC = \frac{\sigma_{School}^2}{(\sigma_{School}^2 + \sigma_{CYP}^2)}$$

Where σ_{School}^2 is the variance at the school level, and σ_{CYP}^2 is the variance at the CYP level.

The 'estat icc' command within Stata© 17 will be used to obtain the ICC estimate and its corresponding confidence interval from the empty multilevel model¹³.

¹³ This has already been estimated on baseline data

Additionally, the ICC will be estimated from the primary analysis model, which includes covariates and other predictors, to assess the impact of adjusting for these variables on the clustering effect.

2.3.11 Presentation of outcomes

Considering the use of a multilevel model, we will use the effect size for cluster-randomised trials adapted from Hedges (2007) as below:

$$ES = \frac{(\bar{Y}_T - \bar{Y}_C)_{adjusted}}{\sqrt{\sigma_S^2 + \sigma_{error}^2}}$$

- $(\bar{Y}_T - \bar{Y}_C)_{adjusted}$ is the mean difference between both arms adjusted for baseline characteristics;
- $\sqrt{\sigma_S^2 + \sigma_{error}^2}$ is the estimated population standard deviation obtained from an 'empty' multilevel model with no predictors.

Consequently, the effect size (ES) quantifies the portion of the population's standard deviation attributable to the intervention, as Hutchison and Styles (2010) outlined. Additionally, a 95% confidence interval for the effect size, adjusted for the clustering of pupils within schools, will be provided. Effect sizes will be computed for each of the estimated regressions.

3 Embedded QED study on targeted intervention

3.1 Design overview

A QED study, using a propensity score matching design, will be embedded within this trial to examine the targeted element of the intervention. In the intervention arm, some staff are given advanced training (Diploma level) to identify a more vulnerable CYP subgroup and provide extra targeted support. This individual intervention is estimated to be provided to about 75 CYP per school, 15 CYP per year group. In the main trial analysis, this group of CYP in Year 8 would become subsumed into the overall intervention group, with all baseline and follow-up data collected on outcomes included in the main trial. Staff who participate in the diploma training will already have identified most young people who would potentially benefit from more intensive support and, in the early stages of training, will be provided with tools to identify any additional young people. By the time of follow-up, at 15 months, this cohort of young people would have been identified and received at least nine months of intervention.

Assuming this group of vulnerable young people is about 15 per school, with a consent rate of 80%, the effective sample size will be 12 per school. Assuming our original aim of 100 schools in the trial, this gives 1,200 CYP across all schools, 600 in the treatment arm matched to 600 in the control arm.

The outcomes for this study will be the same individual pupil-level primary and secondary outcomes as for the main trial, for those that are provided with this individual or small group support in Year 8: the primary outcome is externalising behaviour at pupil level measured by the Strengths and Difficulties Questionnaires (SDQ) – Combined Conduct and Hyperactivity Scale. The secondary outcomes at pupil levels consist of internalising behaviour, prosocial behaviours, total difficulties, non-psychotic psychological distress, well-being, sense of connectedness, exclusions and suspensions, and school attendance.

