There are two levels of participation for CYP in the intervention arm of the study. At a whole school level, the intervention targets school staff who will implement structural changes in policies and practices that ultimately impact all CYP in that school. Outcomes will be measured for a single-year group (Year 8).

At a targeted level, one aspect of the intervention involves training diploma practitioners who will target a sub-group of CYP across the school with a trauma history and provide tailored support. This sub-group of CYP is made up of children who already receive targeted support within the school and so will continue to do so but making use of new skills and knowledge provided by the intervention. Additionally, the measurement tools diploma delegates access through TISUK sessions (ACEs/resilience questionnaire/developmental deficit and gang affiliation checklists and school bonding survey) are integrated into this process.

As this population is only identified in intervention schools, a study within a trial (SWAT) will be undertaken focussing on those identified for this additional support who are in Year 8 (and so are already included in the outcomes measurements for the trial). As the control group cannot be randomised, a quasi-experimental design is appropriate creating a control group using a propensity score matching (PSM) approach. Section 4.1 and Appendix 2 discuss this in detail.

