Appendix - Table 2: Sample size calculations - QED

		PARAMETER
Minimum Detectable Effect Size (MDES)		0.17
Pre-test/ post-test correlations	level 1 (participant)	n/a
	level 2 (cluster)	n/a
Intracluster correlations (ICCs)	level 1 (participant)	n/a
	level 2 (cluster)	0.03
Alpha ¹⁸		0.05
Power		0.8
One-sided or two-sided?		Two
Average cluster size (if clustered)		12
Number of clusters ¹⁹	Intervention	50

¹⁸ Please adjust as necessary for trials with multiple primary outcomes, 3-arm trials, etc., when a Bonferroni correction is used to account for family-wise errors.

¹⁹ Please state how the data is clustered, if there is any clustering (e.g. by delivery practitioner or setting).

		PARAMETER
	Control	50
	Total	100
Number of participants	Intervention	600
	Control	600
	Total	1,200 (without weighting)

A QED study, using a propensity score matching design, will be embedded within this trial to examine the targeted element of the intervention. In the intervention arm, some staff are given advanced training (Diploma level) to identify a more vulnerable CYP subgroup and provide extra targeted support. This individual intervention is estimated to be provided to about 75 CYP per school, 15 CYP per year group. In the overall analysis, this group of CYP would become subsumed into the overall intervention group. Staff who participate in the diploma training will already have identified most young people who would potentially benefit from more intensive support and, in the early stages of training, will be provided with tools to identify any additional young people. By the time of follow-up, at 15 months, this cohort of young people would have been identified and received at least nine months of intervention.

Selection of the comparison group and identification assumptions

An issue that arises is that while we can identify members of this group in the intervention arm of the study by asking for the details of those who receive additional support at six monthly intervals, we cannot identify members in the control arm because there are no set parameters regarding who would be eligible for additional support. As such, we do not have two randomised groups to compare. To address this, we propose to use a quasi-experimental approach, Propensity Score Matching (PSM), to derive an appropriate group for comparison.

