The expected outcomes within the first 5-6 months include increased knowledge, understanding, and skills among staff; enhanced staff support structures and changes in school policies and procedures; improved mental health and well-being, reduced exclusions, and increased engagement among students.'

Further information on the intervention can be accessed here: <https://www.traumainformedschools.co.uk>

This programme will be evaluated through an efficacy trial, a two-arm and a cluster-randomised controlled trial (cRCT). The trial is clustered at the school level as the programme is a whole-school intervention. Every school that signs up to participate in the trial will have an equal probability (50%) of being assigned to the treatment or control groups. In addition, the trial is complemented by an Implementation and Process Evaluation (IPE) and an embedded quasi-experimental design (QED).

The main focus of the process evaluation will be to accurately assess the extent to which the intervention is implemented as intended throughout the school, ensuring fidelity to the intervention's principles. In addition to fidelity, other dimensions to test are dosage, responsiveness, quality, and reach.

The intervention comprises two participation levels for children and young people (CYP). At the whole school level, staff implement structural changes affecting all CYP, with outcomes measured in Year 8. At a targeted level, diploma practitioners provide tailored support to a subgroup of CYP with trauma history. A Study Within a Trial (SWAT) focuses on Year 8 CYP for additional support, employing a quasi-experimental design with propensity score matching (PSM) due to non-randomised control group selection (covered in section 3 below).

2 Main trial on whole school intervention

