2.1 Design overview

This efficacy trial adopts a two-arm, two-level design with pupils clustered into schools. The unit of randomisation is the school. All pupils in Year 8 in the participating schools undertake baseline tests from November 2023 to January 2024 and outcome tests at the follow-up stage in March 2025. The schools within the control group continue to function according to business-as-usual. There is no waitlist design in this trial.

The randomisation process adopts the minimisation approach considering whether the percentage of students eligible for free school meals (FSM6) at each school fell above or below the median percentage of FSM6 across all schools in the sample. More detail is discussed in the next section.

The randomisation process was executed by colleagues from the University of Kent, operating independently from the evaluation team at Ipsos UK. The University of Kent was provided with a list of schools without school names but marked with ID codes, ensuring they could not discern the schools' identities, thus maintaining blindness during the randomisation procedure. The randomisation procedure occurred in two phases: one in early December 2023 and another in January 2024. Initially, the intention was to conduct baseline testing for

all schools in November and proceed with randomisation in December. However, extending the timeline became imperative to accommodate additional time for recruitment, data collection, fieldwork, and the constraints posed by the Christmas break and Ofsted inspections, allowing schools ample opportunity to implement the surveys.

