3.4 Analysis

The primary **research question** is:

- What is the mean difference in externalising behaviour, measured by the Strengths and Difficulties Questionnaire (SDQ) subdomains of Conduct Problems and Hyperactivity, between CYP in intervention settings receiving TISUK training and CYP in control settings receiving business as usual at follow-up?

The secondary **research questions** are:

- What is the mean difference in internalising behaviour, measured by the Strengths and Difficulties Questionnaire (SDQ) subdomains of Emotional Problems and Peer Problems, between CYP in intervention settings receiving TISUK training and CYP in control settings receiving business at follow-up?

- What is the mean difference in prosocial behaviour, measured by the Strengths and Difficulties Questionnaire (SDQ) subdomain of Prosocial behaviour, between CYP in intervention settings receiving TISUK training and CYP in control settings receiving business-as-usual at follow-up?
- What is the mean difference in Total Difficulties, measured by the Strengths and Difficulties Questionnaire (SDQ) subdomain of Conduct Problems, Hyperactivity, Emotional Problems and Peer Problems, between CYP in intervention settings receiving TISUK training and CYP in control settings receiving business-as-usual at follow-up?
- What is the mean difference in non-psychotic psychological distress, measured by the General Health Questionnaire (GHQ), between CYP in intervention settings receiving TISUK training and CYP in control settings receiving business as usual at follow-up?
- What is the mean difference in well-being, measured by the Short Warwick Edinburgh Well-being Scale (SWEMWBS), between CYP in intervention settings receiving TISUK training and CYP in control settings receiving business as usual at follow-up?
- What is the mean difference in the sense of connectedness, measured by the School Connectedness Scale, between CYP in intervention settings receiving TISUK training and CYP in control settings receiving business as usual at follow-up?
- What is the mean difference in the percentage of exclusion between CYP in intervention settings receiving TISUK training and CYP in control settings receiving business as usual at follow-up?
- What is the mean difference in the percentage of suspensions between CYP in intervention settings receiving TISUK training and CYP in control settings receiving business as usual at follow-up?

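### The embedded quasi-experimental study is said to examine the targeted support, but its contrast estimates the whole-school programme and the targeted support combined

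*SAP*

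**What the plan says.** **Aim.** SAP 3.1 opens with "A QED study, using a propensity score matching design, will be embedded within this trial to examine the targeted element of the intervention". Protocol Appendix 2 gives the same purpose, "to examine the targeted element of the intervention". Protocol 4.1, in its short paragraph on the QED, puts it differently: there the purpose is to learn what the intervention does for the group of pupils who get tailored support.

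**Treated pupils.** SAP 3.1 takes Year 8 pupils in intervention schools who are given individual or small-group support. These pupils are also exposed to the rest of the programme. Protocol 3.4 says that at whole-school level "the intervention targets school staff who will implement structural changes in policies and practices that ultimately impact all CYP in that school", and SAP section 1 says "At the whole school level, staff implement structural changes affecting all CYP, with outcomes measured in Year 8".

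**Comparison pupils.** They are matched from the control arm. On the planning figures in SAP 3.1, "this gives 1,200 CYP across all schools, 600 in the treatment arm matched to 600 in the control arm". Of control schools, SAP 2.1 says: "The schools within the control group continue to function according to business-as-usual".

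**Usual support.** Protocol 3.4 says of the supported pupils: "This sub-group of CYP is made up of children who already receive targeted support within the school and so will continue to do so".

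**Research question.** In SAP 3.4 and Protocol Appendix 2 the QED primary question asks for the mean difference in externalising behaviour "between CYP in intervention settings receiving TISUK training and CYP in control settings receiving business as usual at follow-up". This is the trial's ERQ1 unchanged, and it does not mention targeted support.

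**The concern.** The stated aim is about one component, but the two groups differ in more than that component. A supported pupil attends a school where staff have been trained, policies are being changed and webinars are shown, and also gets support from TISUK-trained practitioners. The matched control pupil has none of the TISUK elements. Better matching does not help, because exposure to the whole-school programme is fixed by the arm and not by any pupil covariate.

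What is at stake is how a QED result is read. Under the aim in SAP 3.1, a favourable estimate would naturally be presented as evidence about the targeted support. A funder deciding whether individual support is worth paying for on top of the whole-school programme would be relying on a figure that cannot answer that question.

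**Working it through.** **1. The plan's own figures.** Sample: 15 pupils per school × 0.80 = 12; 12 × 50 schools = 600 per arm; 1,200 in total, as SAP 3.1 states. After randomisation: 78 schools × 12 = 936, as in SAP Table 8.

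MDES in the randomisation column of SAP Table 8, using the two-level formula in SAP 2.2 without covariates, J = 78 schools, m = 12, ICC 0.015 and P(1 − P) ≈ 0.25:

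- SE = √[0.015/(0.25 × 78) + 0.985/(0.25 × 78 × 12)] = √(0.000769 + 0.004209) = 0.0706.
- MDES = (1.960 + 0.842) × 0.0706 = 0.198 with normal multipliers, and 0.200 with t multipliers. The table gives 0.20.

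**2. What the contrast identifies.** In pupils of the kind selected for support, let

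- w = the effect of the whole-school programme;
- t = the added effect of targeted support from TISUK-trained staff, over the support such pupils would otherwise get.

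Supported pupils in intervention schools carry w + t. Matched pupils in control schools carry neither. With perfect matching and additive effects, the QED estimates w + t. One contrast cannot determine two unknowns.

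**3. Whether another planned analysis separates them.**

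- The robustness checks in SAP 3.4.3 concern matching and weighting methods, balance, unobserved selection and falsification. None changes who is compared with whom.
- SAP 3.4.6 rules out further QED analyses beyond the subgroups and robustness checks.
- The main limitation named in SAP 3.3 is unobserved covariates. The bundling of the two elements is not mentioned.
- The intervention-arm regression in SAP 2.3.4 uses process measures of delivery. It names no pupil-level receipt of targeted support.
- Subtracting the main-trial estimate does not recover t. That estimate averages over all Year 8 pupils, includes the supported ones (SAP 3.1), and need not equal w in vulnerable pupils.

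**4. Illustration of size.** Values of t that fit a QED estimate of 0.20 SD, from t = 0.20 − w:

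| w | t |
|---|---|
| 0 | 0.20 |
| 0.094 (main-trial MDES at randomisation, SAP Table 4) | 0.106 |
| 0.20 | 0 |

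Chance that the QED is significant when t = 0, from Φ(w/0.0706 − 1.96):

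| w | w/SE | Probability |
|---|---|---|
| 0.05 | 0.71 | 11% |
| 0.094 | 1.33 | 27% |
| 0.20 | 2.83 | 81% |

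The values of w are assumptions chosen to show the range. The documents give no expected whole-school effect.

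**The case against.** The strongest reply is that the QED is coherent as designed. Protocol 4.1 asks about the effect of the intervention on the targeted group, the research question openly sets intervention settings against control settings, and SAP 3.1 restricts the analysis to pupils who were given support. That is a sensible question and the design can address it. This stands, and it settles the form of the point: the fault is the conflict between that aim and the one in SAP 3.1 and Appendix 2. The QED is not uninformative.

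Several stronger readings are tempting, but the documents do not support them.

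- *Control pupils get no targeted support.* Protocol 3.4 says these are children already receiving support in school, and Protocol 3.2 maps the specialist support available as part of business as usual. Matched controls may have usual targeted support. That blurs the meaning of t further; it does not isolate t.
- *The QED will come out positive even if the support adds nothing.* The estimate would be centred on w, but at w = 0.094 it would be significant only about 27% of the time.
- *About half of a 0.20 effect is whole-school effect.* That follows only from choosing w near 0.10. An MDES is a detection limit, not an expected effect, and the whole-school share could be anything from none to all.
- *The QED could be repaired to show what the diploma adds.* Protocol 2.3 has diploma practitioners also working with senior leaders on culture, policy and practice, so the diploma feeds w as well as t. No pupil-level contrast isolates its value.

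**Conclusion.** The point holds as a mismatch between the stated aim and the estimand. As planned, the QED estimates the combined effect of the whole-school programme and TISUK-trained targeted support, against business as usual, in pupils like those selected. It cannot say how much is due to the targeted support. Unless the whole-school effect is zero in these pupils, the estimate is not t.

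The illustrative figures assume additive effects, valid matching, 78 schools with 12 pupils each and an ICC of 0.015. The identification argument does not depend on those figures. The trial's primary analysis is unaffected; what changes is what the QED may be said to show.

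**What to change.** **Wording.** In SAP 3.1 and 3.4 and in Protocol Appendix 2, restate the objective and primary question consistently with Protocol 4.1: the effect of the whole-school programme plus targeted support, compared with business as usual, among pupils selected for targeted support. Add that the result is not an estimate of the targeted support alone and will not be reported as one.

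**Optional, exploratory.** Add a propensity-weighted comparison of supported and unsupported pupils within intervention schools. It needs no new collection: all Year 8 pupils are surveyed (SAP 2.1), and a list of supported pupils is part of the monitoring data (Protocol Table 7). With 40 schools, 12 against 12 per school and ICC 0.015, its MDES would be about 2.80 × √[0.985 × (1/480 + 1/480)] = 0.18. That assumes the same whole-school effect in both groups, no spillover and no residual selection. The limits should be stated with it. SAP 3.3 says there are no set criteria for who is eligible, so the comparison is open to confounding by unmeasured need, and needier pupils may look worse and hide a benefit. It is also open to spillover, and it does not isolate the value of the diploma training.

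**Cost.** Edits to two documents, one extra weighted model if the option is taken, and a more modest claim for the QED.
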